**Unique Protocol ID: 15-960**

**Study Protocol**

**Date: March 29, 2018**

**A strong finances and families are the foundation of wellbeing for individuals, families, and communities.** Low income families tend to experience chronic financial stress and are therefore, are at a higher risk for individual psychological and physical distress, relationship problems and dissolution, and parenting challenges, all of which in turn contributes to financial stress and economic instability. Financial stress and unstable economic conditions affect adults' individual well-being (e.g., substance abuse, depression and anxiety disorders), couple relationships (e.g., interpartner hostility, relationship dissatisfaction), and parenting, and children's emotional and physical health (Falconier, 2010; Kwon, Rueter, Lee, Koh, & Ok, 2003; Puff & Renk, 2014). Negative mental health outcomes can contribute to economic hardships through negative job outcomes. Recent research suggests that couple relationship education for disadvantaged couples could develop and sustain healthy relationships (Hawkins & Erickson, 2015). However, any efforts to intervene in the relationships and marriages of low income groups should directly address the chronic financial stress they experience and its permeating negative effects on different domains of their lives. Low-income couples might benefit more from a relationship education approach that helps them improve their relationship skills in the context of their financial stress and economically disadvantaged realities and connects them with the social services they need and with job/career enhancement resources that move their families towards economic stability and mobility. The interconnectedness of all of these factors influencing couple's relationships is important to address in a comprehensive intervention that integrates treatment components and takes into consideration the learning happening in other domains while focusing intervention in a specific treatment element or goal.

We target couples who live in Northern Virginia and Prince George's County and [name]. Even though these areas have high performing health and socio-economic outcomes for both the capital area and the nation, demographics have changed significantly in the past decade and disparities exist among subpopulations and low-income families. Overall high performing indicators may mask the true number of families that are seriously financially distressed and how racial/ethnic minorities are disproportionately more affected.

This project is funded by the Department of Health and Human Services (HHS), Administration for Children and Families (ACF), Office of Family Assistance (OFA) under the Healthy Marriage and Responsible Fatherhood (HMRF) program. This project is developed and conducted by Project Director, [name]. at Virginia Tech and Associate Director, [name]. at University of Maryland. Both universities are collaborating for this project and University of Maryland is a subawardee of Virginia Tech. In addition, Virginia Tech has subcontracted with SkillSource Group, Inc. for delivery of the intervention and University of Maryland has contracted with Family Services, Inc. for delivery of Services. Services will be delivered at Virginia Tech, Family Service Inc, University of Maryland, and in agencies in which we have agreements to use their space (City of Bowie in Bowie, MD and Ebenezer Baptist Church, Alexandria, VA) The funding agency requires the grantee to have an independent local evaluator and for that purpose Virginia Tech has contracted with AVAR Consulting, which will be involved in the implementation and outcome evaluations. Avar Consulting as well as [name] and [name] will only use the database without participants' identifying information to conduct their outcome evaluations.

The project employs a randomized control trial (RCT), in which 360 couples are assigned to the intervention group and 360 couples to a control group between June 1, 2016 and September 30, 2020. Our approach integrates three components (1) a 20-hour evidence-informed couple group program called TOGETHER workshop that integrates relationship education and financial literacy skills, (2) case management (assessment of participant needs, development of Individual and Couple Development Plan, referrals for social and mental health services, and referrals and coordination with job and career enhancement services, linking and coordination of all services as needed), and (3) job and career enhancement services for those who need the services.

The main goals of this project are to promote healthy couple relationships and economic stability and mobility for low-income couples in Northern Virginia, Prince [name], and [name]. The main objectives are: 1) improve personal wellbeing; 2) improve

**couple's relationship skills; 3) improve parenting and co-parenting; 4) improve financial literacy and capability; and 5) improve employability, job placement, and retention skills.**

Short-term outcomes of this project's core intervention are expected immediately after completion of the last session of the 20-hour relationship/financial education program (TOGETHER) whereas medium-term outcomes are anticipated six months after that last session. Expected measurable outcomes among program participants for objective 1 (improved personal well-being) include increased frequency of positive stress management, reduced psychological distress, decreased financial stress. Expected measurable outcomes for objective 2 (improved couple's relationship skills) include increased frequency of positive communication behaviors, increased frequency of positive conflict management behaviors, increased frequency of positive dyadic stress management, increased frequency of conjoint problem solving behaviors, increased satisfaction with couple's relationship, and increased comfort with financial styles and roles. Expected measurable outcomes for objective 3 (improved parenting and co-parenting) include increased frequency of positive parenting behaviors, increased closeness to children, and increased satisfaction with co-parenting. Expected measurable outcomes for objective 4 (improved financial literacy and capability) include increased financial literacy skills, increased financial self-efficacy, decreased use of alternative financial services, and increased financial management behaviors. Finally, expected measurable outcomes for objective 5 (improved employability, job placement, and retention) include decreased perceived barriers to employability, increased intentions and motivations for work, increased confidence in job skills, and increased employability, employment status, and retention.

**The research team plans to use the study results to apply for future grants, write reports for the funding agency, submit manuscripts for publications, and disseminate results through conferences and public media appearances, as requested. Participants' identities will always be protected in any dissemination of study findings.**

**Target population in the proposed project is low-income couples, but any couple that wants to participate in the program will be accepted as long as they meet the eligibility criteria: residing in Northern Virginia and Prince George's County and Montgomery County in Maryland, married or cohabiting for at least a year, 18 years of age or older, and English-speaking. Exclusion criteria includes both partners being retired, physical domestic violence (defined as behaviors that frighten, terrorize, manipulate, hurt, humiliate, blame, often injure, and sometime kill, a current or former intimate partner) or feeling unsafe with partner in the last six months, current diagnosis of a severe psychiatric disorder that required hospitalization in the last 12 months, cognitive impairment, or/and severe untreated substance abuse disorder. Couples can participate as long as both partners consent to be part of the program.**

**To conduct the randomized control trial, 360 couples will be enrolled (180 from Northern Virginia and 180 from Montgomery County, Maryland) for the intervention group and 360 couples (180 from Northern Virginia and 180 from Montgomery County, Maryland) for the control group. Within each group (intervention and control), 20 couples will be enrolled in Year 1 (7/1/16-9/30/16), 100 in Year 2 (10/1/16-9/30/17), and 100 Year 3(10/1/17-9/30/18), 100 in Year 4 (10/1/18-9/30/19), and 40 in Year 5 (10/1/19-9/30/20).**

**Recruitment activities will begin on June 1, 2016. Activities will include producing and distributing flyers, brochures, and posters and/or giving presentation in schools, churches, faith-based community centers, child support agencies, TANF offices, WIC agencies, Head Start programs, Healthy Start program, child welfare agencies, community centers, libraries, stores, barber shops, employment centers, Virginia Tech and University of Maryland clinics and cooperative extension centers, and community events. The Women's Center and Family Services Inc. will concentrate on marketing and recruitment efforts from the network of providers and partner organization they are part of. In addition, graduate students will be responsible for setting up social media outlets that will be used for marketing and recruitment purposes and posting calendars with program activities. The program will also be advertised through its own website ([www.togetherprogram.org](http://www.togetherprogram.org)) and online ads.**

**The grant program manager will be responsible for overseeing all marketing and recruitment activities. These activities will be conducted by Virginia Tech and University of Maryland graduate student assistants and volunteers as well as designated administrative staff in The Women's Center and Family Services, Inc. (community partner agencies contracted for this project). The flyer and the brochure have been attached.**

**Low income families often experience greater social and economic challenges such as unemployment, poverty, low levels of education, poor job skills, and financial instability. They have limited access to resources to establish healthy relationships and economic stability due to limited social networks, skills and opportunities.**

The target geographic areas in this proposal are Northern Virginia (VA) and Prince George's County Montgomery County, Maryland (MD). Even though these areas have high performing health and socio-economic outcomes for both the capital area and the nation, demographics have changed significantly in the past decade and disparities exist among subpopulations and low-income families who struggle even more than before the last recession which occurred between December 2007 lasting until June 2009 (U.S. National Bureau of Economic Research). Although the median household income is high for Northern VA and Montgomery Co., MD (\$93,100 - \$122,238), the cost of living in these areas was 40% above the national average according to the 2010 U.S. Census and self-sufficiency standard for families has increased significantly in the last decades. For example, in Montgomery Co for a family of three the self-sufficiency standard doubled from \$32,016 in 1994 to \$68,086 in 2010 and contrasted markedly with the federal poverty level of \$17,600 for a family of three and the minimum wage job of \$12,792 for the annual full-time salary. Fairfax Community Action Board recommended using the number of people living in households with incomes below 200% as a better indicator of the level of need in those geographic areas as that indicator more closely approximates the level below which people have difficulty meeting their needs without some kind of assistance. In Fairfax Co 16.8% of residents and 18.3% of residents in Montgomery County live in households with earnings less than 200% of poverty, which indicates clearly the large number of families in this region that cannot meet their financial needs and that are at risk for individual, parenting, and relationship problems.

Couples interested in participating will be screened in person or over the phone by the trained project staff at the Northern Virginia Center of Virginia Tech, University of Maryland, Family Services, Inc., City of Bowie building or Ebenezer Baptist Church in Alexandria (VA). Staff must ask the couples for verbal permission before asking screening questions. If they meet eligibility criteria, they will be given an appointment with a case manager at any of the previously mentioned locations if the couple lives in Northern Virginia, Prince George's County or [name]. When the first appointment is made, participants will be provided with the information about program procedures. Potential participants will be offered the possibility of receiving a copy of the consent form by email or mail for their review prior to this appointment. This first appointment with the case manager is called "Intake and Enrollment Meeting." When the couple arrives for this meeting, the very first step that the case manager will take is describing the program TOGETHER in detail to the couple, providing them with an opportunity to ask any questions they may have. Once both partners in the couple say that they want to participate, the case manager will give each of them a hard copy of the consent form. The case manager will instruct each partner to read the consent form in detail and once again will invite partners to ask any questions they may have. The consent form will have every detail of the program including the risks and benefits. Additional simple instruction tools will be used to help participants understand the study procedures. Case managers will remind both members of the couple that their participation is voluntary and that at any time they may discontinue participation. Each partner will sign two copies of the consent, one for them to keep and another one for the program staff to store in a safe, locked cabinet.

**The Program Manager of this project will be overseeing the process of obtaining and maintaining informed consents from subjects. The Program Manager will inform the Principal Investigator (Project Director: [name]) and the Co-Investigator (Associate Project Director: [name]) of any problems that may arise. PI will also randomly check the process. In addition, an independent evaluator will be collecting data for evaluation of the program implementation and will alert the Principal Investigator and Co-Investigator of any deviations from the protocol for obtaining consent that is delineated in the Intake and Enrollment Protocol.**

**The consent process will take place in the offices of the Northern Virginia Center of Virginia Tech, the University of Maryland, Family Services, city of Bowie building, and Ebenezer Baptist Church in Alexandria, VA Inc. with the case manager that is meeting with the couple for the Intake and Enrollment Meeting. Family Services, Inc. Consent process will take place in private offices within each of those locations with program case managers (all currently hired and supervised by Family Services, Inc.)**

**A case manager will hold an intake and enrollment meeting with every couple interested in participating in the program and that meets inclusion criteria. This meeting will take place before a couple participates in any activities of the TOGETHER program. During this meeting, the case managers will (a) explain the program procedures, obtain voluntary, informed written consent for program participation, (b) screen for domestic violence, (c) enroll participants and present overall program description, (d) collect and enter participant's demographic data in the online participant system for randomization, and (e) assign couples to the intervention or control group (see 5.1. for further details about this Intake and Enrollment Meeting).**

When the project staff makes the first meeting appointments with case managers, the description of study procedures will be provided for potential participants to review the program prior to the first meeting. As noted earlier, potential participants will be given the opportunity of receiving by email or mail a copy of the consent form for them to review prior to the Intake and Enrollment Meeting (first meeting with the case manager). At the first meeting, the case manager will take the time to describe every aspect of the program and will give time for the couple to ask any questions they may have. Flowcharts and Schedules of Intervention and Control Group Couples will be provided to facilitate understanding of the program. Then the couple will be given time to read the consent form in detail and, again, ask any questions they may have. In the event that the couple says that they need more time to read the consent form, another appointment will be made to complete the intake and enrollment meeting. We will also be emailing an electronic copy of the consent form to those couples that want to receive such a copy before the Intake and Enrollment Meeting.

This study is being funded by a Healthy Marriage and Responsible Fatherhood (HMRF) grant by the Office of Family Assistance, Administration of Children and Families, U.S. Department of Health and Human Services. The funding agency requires all HMRF grantees to enter information into a secure system called the Information, Family Outcomes, Reporting, and Management system (nFORM). The information requested to enter is about (a) program operations (e.g., aggregated data without personally identifiable information on outreach and recruitment activities, enrollment numbers, staff qualifications and training, staff supervision and observation, and implementation challenges); (b) services (e.g., case management activities, workshop attendance, and referrals); (c) participants' contact information, demographics, and outcome measures. The funding agency also requires the use of tablets for collecting data from participants. This tablet will also be used to collect additional participants' outcome measures through Qualtrix. Please see Sections 5 and 8 for a further description of the nFORM system and data collection through Qualtrix.

See Intervention Group Flowchart for Participants document and Control Group Flowchart for Participants document in Attachments to follow each step of the procedure more easily.

Besides nFORM and Qualtrix, two additional databases will be used to collect information about participants and about program operations. One of them is called ICS database and is used to collect contact information about potential participants and screen them to see if they meet inclusion criteria before enrollment in the program. The section where identifying information such as participants' name, phone number or email address are stored separately from the answers to the screening questions. This ICS database is cleaned once a month so that all contact information is erased and only the number of participants that qualified or didn't qualify for the program can be counted. This ICS database complies with all VT requirements. It is an external service with proper SSL or similar encryption on the login and data collection pages. Only trained program staff (graduate assistants, program managers, principal investigators, and quality assurance and operations coordinators will have access to this database. The second database is called Participant Tracking System (PTS). PTS is also compliant with all VT requirements for databases that collect participants' information as it is an external service with proper SSL or similar encryption on the login and data collection pages. PTS will be used for the purposes of automated randomization and scheduling meetings. The system is being developed and it may serve further functions in the future. We will request IRB permission first before it can serve other purposes. For the time being PTS will be used to collect contact information from participants to randomize according to place of residence and can help scheduling meetings. Trained program staff will have access to this database and this includes case managers, program manager, group facilitators, graduate assistants, quality assurance and program operations coordinators, and principal investigators. However, access will be restricted to each of these users so that participants' contact information is protected. PTS will be used for scheduling not only meetings for participants but also staff meetings (e.g., between case managers and group facilitators to discuss workshop concerns). PTS will not collect any information involved in the pre-, post- and follow up surveys (nFORM + Qualtrix) and therefore, it won't have the outcome data involved in data analysis. Same is true of the ICS database.

#### Initial Contact and Screening

Individuals interested in participating in the program will dial a 1-800-number to the program staff or may visit the program at any of the program locations (Virginia Tech, University of Maryland, and Family Services, Inc.). Program staff will (a) collect contact information from the individual interested in participating, (b) describe the program and the potential compensation, (c) ask for verbal consent to proceed with screening questions, and (d) perform a 10-minute inclusion screening process of the potential participant and his/her partner. The program staff will speak with each partner during the call or visit if both partners are available. Otherwise, the program staff will collect information and screening information about both partners with the only partner that is present. However, when asking questions the staff will clarify that the caller is not required

to identify who of the two members in the couple does not meet eligibility criteria. Staff members administering the screening questions will obtain verbal consent to ask questions from the potential participant and will clarify that all screening data will be deleted after 30 days. All potential participants who are eligible after the initial screening and agree to participate will be scheduled for an Intake and Enrollment meeting with the case managers at Virginia Tech, The University of Maryland (UMD), Family Services Inc. (FSI), the city of Bowie, or Ebenezer Baptist Church in Alexandria, VA (see next section). The study procedure will be described and additional information will be sent upon request. Potential participants will be offered the consent form for them to review prior to the Intake and Enrollment meeting, given either in person or mailed to them upon request (Attachments: Initial Contact and Screening Script). ICS data will be saved in the ICS database.

**Possibility of ICS Procedure online: Summary of Online Initial Contact and Screening (ICS) Procedure**

Potential participants who are interested enrolling in the Together Program have the option of completing the screening with an ICS staff member online as well. If potential participants choose to complete the online screening, they can be directed to the screening in two ways: via a link an ICS staff member emails them after the potential participant and the ICS member review the Together Program Overview information together on the phone or via the Together Program website after the potential participant reviews the Together Program Overview information via the website.

Potential participants who obtain their information via the Together Program website will automatically be directed to the online screening page. Potential participants will review the Together Program Screening Information (please see below) prior to agreeing to the terms to continue with the online screening.

"Thank you for your interest in participating in TOGETHER program. You just read the overview of TOGETHER program, received an overview from one of our staff members over the phone, or watched our informational video.

Now you understand the program. We would like to ask you some questions about you and your partner to find out if our program can benefit you and your partner. Completing the questionnaire does not guarantee your eligibility. This screening process will take about 15 minutes to complete.

First, we will ask you to provide contact information and the best time to reach you and your partner in order to follow up. Then, we will ask some questions about you and your partner including your health and relationship. These questions address the issues of mental health, domestic violence, and substance abuse. Our program is not suited for everyone. These questions will help us to determine if you are eligible and if it is safe for you and your partner to participate in this program. It is important for you to have privacy when you are answering the screening questions. If you have any questions or would prefer to complete the screening process over the phone, you may contact the Together Program at [name]. You can choose to stop answering the questions if you do not want to participate.

Any identifiable information that you give us now will only be used to see if you are eligible to be in this program. After 30 days, we will destroy our records of your personal information.

Should you have any questions about this study, or if you wish to complete the screening process via the phone you may contact the TOGETHER program at [name].

By participating in this screening process, you are indicating that you are at least 18 years of age; the study has been explained to you; your questions have been fully answered; and, you freely and voluntarily choose to participate in the screening process."

Once potential participants have agreed to continue with the online screening, they will be prompted to enter information about themselves and their partner. This information includes their first and last names, phone numbers, and emails. Potential participants will also fill out their preferences for when they would like to be contacted, what location they would like to participate at, and the best days and times they are available for workshops. They are also asked to indicate how they heard about the Together Program.

Once potential participants fill out the demographic information, they will complete the online screening. Once they have completed the screening, they will receive the following message: "Thank you for completing the questionnaire! A trained staff member will review your answers and will be in touch with you by email or phone within 3 business days. We may contact you with additional questions. If you have any questions, you may contact the Together Program at [name] or [[contact]](mailto:[contact]) "

After potential participants complete an online screening, an email from "Together Screening" will be sent to the Together Screening Gmail Account with a notification message that a potential participant has submitted a survey. The notification will also give an overall score for the potential participant. The message will appear as the following:

"A potential participant has completed the online screening. This participant received a score of X  
Note: A score of 0 indicates there were no issues identified by the participant, any score 1 or above indicates participant has confirmed potential exclusionary criteria.

\*Please review response for completeness to ensure participant eligibility.

Please enter all information into ICS (using screening option 2) and contact the participant." Designated ICS staff (e.g., ICS Coordinator, Case Managers) will be responsible for checking the email account every 1-2 business days to review any recently submitted surveys.

Following this message will be a summary of all the potential participant's responses as well as the contact information they have provided. Designated ICS staff will be required to look through each of the responses to assess if there are any screening concerns that need to be addressed prior to calling the potential participant to schedule an Intake and Enrollment (IE) meeting.

If there are no screening concerns, meaning that there is a score of "0," ICS staff insert the potential participant's contact and screening information into the ICS system and place the potential participant in the "Eligible and Further Action Needed" category. Once the potential participant is inserted into the ICS system, ICS staff will call to inform the potential participant that they are eligible for the program and to set up a day and time for the IE meeting.

If there are screening concerns, meaning that there is a score of "1" or higher, designated ICS staff will insert the potential participant's contact and screening information into the ICS system (refer to Appendix A for a list of questions taken directly from the online survey) but will need to follow up via phone call with the potential participant about the specific concerns. Designated ICS staff will refer to Section 9 in the Initial Contact and Screening Protocol for ineligibility requirements.

If a potential participant is ineligible due to their answers to the online survey (where no follow-up via phone call is needed), designated ICS staff will need to inform the potential participant that

they are ineligible for the program. Designated ICS staff will inform the potential participant via email and will provide the potential participant with referrals.

If ICS staff is unsure about specific concerns and/or questions, he or she should consult their supervisor.

Emails containing contact information and answers to screening questions will be deleted immediately after the information has been entered into the ICS database. The answers to screening questions collected through Qualtrix surveys will be deleted once a month.

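### The online screen asks about partner violence, but the protocol describes no check that the reply channel is private, is unclear on who is phoned and who is emailed, and emails answers together with identifiers

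*Protocol*

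**What the plan says.** All of this comes from the Protocol; the SAP does not touch it.

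- **Content of the form.** The applicant is told that the questions cover mental health, domestic violence and substance abuse, and is advised: "It is important for you to have privacy when you are answering the screening questions". The eligibility paragraph makes physical domestic violence, or feeling unsafe with the partner in the last six months, an exclusion.
- **Contact details.** One applicant enters names, phone numbers and emails for both partners. On how to be reached, the text says: "Potential participants will also fill out their preferences for when they would like to be contacted". The closing message announces contact by email or phone within 3 business days.
- **Staff notification.** Each submission triggers an email to a program Gmail account with a score. Of that score it says "any score 1 or above indicates participant has confirmed potential exclusionary criteria". The email then continues: "Following this message will be a summary of all the potential participant's responses as well as the contact information they have provided". Staff check the account every 1-2 business days.
- **Reply to the applicant.** At a score of 1 or higher, staff enter the data "but will need to follow up via phone call with the potential participant about the specific concerns". A later paragraph opens a second route: "If a potential participant is ineligible due to their answers to the online survey (where no follow-up via phone call is needed". For that group, "Designated ICS staff will inform the potential participant via email and will provide the potential participant with referrals".
- **Storage.** The ICS database description, given three times in the Protocol, says that "identifying information such as participants' name, phone number or email address are stored separately from the answers to the screening questions".

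**The concern.** An applicant who discloses violence online may share a phone or mailbox with the partner concerned, or the partner may be able to see it. A call about specific answers, or an email with referrals, could then reach the wrong person. The Protocol is alert to this hazard elsewhere: it advises privacy while the form is filled in, and it interviews each partner alone at the Intake and Enrollment Meeting. The online reply step has no comparable precaution in the supplied text.

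The staff notification is a second exposure. It places a named person's answers on violence, psychiatric history and substance abuse in a mailbox that does not appear in the Protocol's account of database encryption and access limits. What is at stake is participant safety and confidentiality, not an estimate or an error rate.

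**Working it through.** No arithmetic applies. The check sets the passages side by side.

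**1. Can a violence disclosure lead to a reply?** Yes. The form asks about violence, and violence or feeling unsafe is an exclusion. A positive answer therefore leads either to a call or to a finding of ineligibility.

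**2. Is the reply channel checked?** The form collects phone, email, preferred times, preferred location, workshop availability and how the applicant heard of the program. None of these establishes that a number or address is private. Neither the call step nor the email step adds a check. The procedure is headed a summary, however. The full ICS Protocol, its question list and the Domestic Violence Protocol are separate documents that were not supplied. The gap is established for the supplied text only.

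**3. Who is phoned and who is emailed?**

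| Statement in the online ICS section | Consequence |
|---|---|
| A score of 1 or above means a potential exclusion has been confirmed | Every scored exclusion answer gives at least 1 |
| A score of 1 or higher will need a phone follow-up | Every such applicant is called |
| Some applicants are ineligible on their answers with no call needed | Some ineligible applicants are not called |

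Read literally, the first two rows leave nobody for the third, unless some ineligibility answers are not scored or some scored answers are exempt from the call. The text says neither. It refers staff to Section 9 of the ICS Protocol for the ineligibility requirements, and that section was not supplied. So the supplied text cannot show whether a violence answer is handled by phone or by email. The missing privacy check applies to both routes.

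**4. Are answers and identifiers kept apart?** In the ICS database, yes. In the notification email, no: all responses and the contact information are in the same message. The message can wait up to the checking interval of 1-2 business days, and then until entry, when it is deleted. The online answers held in Qualtrics are deleted monthly. The exposure is limited in time, but it arises for every online submission, including those that score 0.

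**The case against.** The strongest reply is that the Protocol breaks none of its own rules. A reader might infer a violation, and the documents do not support that. The separation sentence describes storage in the ICS database and does not mention email. The privacy sentence advises the applicant about surroundings while answering and does not govern how results are sent. The combined email is openly provided for, with deletion after entry. This stands. What remains is a mismatch with the purpose of the separation.

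A reader might also infer that violence disclosures are answered by email, or that the email reveals them. Neither is shown. Routing depends on a document not supplied, and nothing says the email gives a reason. Ineligibility alone does not point to violence, since the exclusions also include both partners being retired, psychiatric disorder, cognitive impairment and substance abuse. Referrals could point to it if they are issue-specific, and the text does not say whether they are.

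A third tempting inference is that applicants will hide violence online, so that more such couples reach assignment. The documents give no evidence for this. The Domestic Violence and Child Maltreatment section places an individual structured screen of each partner before randomization, with later discontinuation possible. That screen does not help people turned away online, who never reach it.

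The telephone safeguard, under which callers need not say which partner fails a criterion, is not a fair comparison. It concerns how questions are asked, and the online form's question list was not supplied.

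Finally, applicants are told to expect email or phone contact and are twice offered telephone screening instead. That is a real mitigation, but it leaves the applicant to foresee the risk.

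**Conclusion.** The point holds in limited form, as a low-cost improvement to participant safety and confidentiality:

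- The supplied text describes no check that the reply channel is private, although the form asks about partner violence.
- The phone and email routes are not reconciled with the scoring rule.
- Answers and identifiers travel together to a Gmail account, which is inconsistent with the purpose of separating them in the ICS database.

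The size cannot be given, because the documents report no numbers screened online, flagged or found ineligible. The first two items concern online applicants with a flagged or disqualifying answer; the third concerns every online applicant. No sample size, estimate or analysis changes.

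The first item assumes that the documents not supplied contain no safe-contact step. If they do, it reduces to a request for a cross-reference. The other two rest on the supplied text, although Section 9 of the ICS Protocol may settle the routing.

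**What to change.** 1. Add one item to the online form asking for a safe and private way to be reached, and use that route for all replies.
2. Use a neutral template for the ineligibility email: no reason stated, and any referral list general rather than issue-specific. Withholding referrals until a safe route is given is not recommended here, because it could leave some applicants with none.
3. Limit the staff notification to a record number and the score, and have staff read the answers in the secure system.
4. Reconcile the scoring, call and no-call sentences by stating which answers are handled by phone and which by email. If Section 9 of the ICS Protocol already does this, cite it at that point.

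The cost is one form item, one template, one notification setting and a clarified paragraph, submitted as a minor amendment, plus slightly more staff time per applicant. Enrolment targets and the analysis are unaffected.
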